3.1.2 Rules for Advancement to Cohorts 2-5

Enrollment in Cohort 2 may commence after all three subjects in Cohort 1 have completed 30 days of follow up after AST-OPC1 administration AND the safety data for Cohort 1 have been reviewed by the Data Monitoring Committee (DMC).

Enrollment in Cohort 3 may commence after at least five subjects in Cohort 2 have completed 30 days of follow up after AST-OPC1 administration AND the safety data from Cohorts 1 and 2 have been reviewed by the DMC.

Enrollment in Cohort 4 may commence after at least two subjects in Cohort 2 have completed 30 days of follow up after AST-OPC1 administration AND if there are no SAEs that would trigger study suspension.

Enrollment in Cohort 5 may commence after at least two subjects in Cohort 3 AND at least five subjects in Cohort 4 have completed 30 days of follow up after AST-OPC1 administration AND if there are no SAEs that would trigger study suspension.

For the planned DMC reviews noted above, the DMC will recommend whether enrollment of the next dose cohort can commence or whether additional follow up of the current cohort is needed prior to commencing enrollment in the next cohort. The rationale for the 8-day stagger (or the 14-day stagger between consecutive subjects with a C4 NLI) is that nearly all of the potential surgical complications, if they occur, will become clinically evident within the first few days after surgery. Thus, any serious complications (i.e., SAEs) would be evident within the first few days after surgery and would be reported within 24 hours of their occurrence (as required for all SAEs).

In addition, subjects in this study will receive a complete neurological exam and MRI scan for safety monitoring at 7 days after AST-OPC1 injection. The study suspension rules (See Section 7.14.2) include several rules that could be triggered by potential complications of the AST-OPC1 injection procedure, such as: death or unexpected neurological deterioration, evidence of direct spinal cord damage related to the volume of injection, or any CSF infection or inflammation that is more than a transient reaction to AST-OPC1 injection.

3.2 Number of Subjects

A total of 23-35 subjects are planned to receive AST-OPC1. A maximum of 35 of subjects will receive AST-OPC1.

3.3 Investigational Sites

This is a multicenter study with approximately 8 institutions participating.

3.4 Study Duration

Enrollment is expected to take approximately 36 months. The treatment and observation period for individual subjects on this study (excluding long-term follow-up study) is approximately 12 months. The total duration of this study is about 4 years.
4 SELECTION OF STUDY POPULATION

Prior to completing any protocol-specific tests or procedures, the subject will sign informed consent both for the primary protocol AST-OPC1-01 and the long-term follow-up protocol AST-OPC1-02.

4.1 Inclusion Criteria

- 1. Sensorimotor complete, traumatic SCI (ASIA Impairment Scale A) for Cohorts 1, 2, and 3
- 2. Sensorimotor incomplete, traumatic SCI (ASIA Impairment Scale B) for Cohorts 4 and 5
- ISNCSCI Neurological Level of Injury (NLI) from C-5 to C-7 or a C4 NLI with an upper extremity motor score (UEMS) ≥ 1
- 4. From 18 through 69 years of age at time of consent
- 5. Single spinal cord lesion on a post-stabilization magnetic resonance imaging (MRI) scan, with sufficient visualization of the spinal cord injury epicenter and lesion margins to enable post-injection safety monitoring
- 6. Informed consent for this protocol and the companion long term follow-up protocol must be provided and documented (i.e., signed informed consent forms) no later than 37 days following injury
- 7. Able to participate in an elective surgical procedure to inject AST-OPC1 21-42 days following SCI

4.2 Exclusion Criteria

- 1. SCI due to penetrating trauma
- 2. Traumatic anatomical transection or laceration of the spinal cord based on prior surgery or MRI
- Spinal cord lesion with anteroposterior (AP) diameter of the spinal cord < 2 mm at point of maximal compression on a midline sagittal image from a poststabilization MRI
- 4. Any concomitant injury that interferes with the performance, interpretation or validity of neurological examinations, such as multiple spinal cord lesions, brachial/lumbar plexus injury, cauda equina injury or traumatic brain injury
- 5. Any treatment or pre-existing condition that interferes with the performance, interpretation or validity of neurological examinations, such as polyneuropathy, focal or multi-focal neuropathy, myelopathy or radiculopathy

- 6. Inability to communicate effectively with neurological examiner such that the validity of patient data could be compromised
- 7. Significant organ damage or systemic disease that would create an unacceptable risk for surgery or immunosuppression
- 8. Acute, symptomatic pulmonary embolism that would create an unacceptable risk for surgery
- 9. Concomitant use at baseline of other immunosuppressive agents, such as corticosteroids, that would create an unacceptable risk for additional immunosuppression with tacrolimus
- 10. Need for mechanical support of ventilation (ventilator, continuous positive airway pressure [CPAP], bi-level positive airway pressure [BiPAP]), excluding supplemental oxygen, at baseline
- 11. History of any malignancy (except non-melanoma skin cancers)
- 12. Pregnant or nursing women. Female subjects of child bearing potential must agree to prevent pregnancy by the use of contraception for 1 year following AST-OPC1 injection; male subjects must agree to use contraception to prevent pregnancy in any female partners of child bearing potential for 1 year following AST-OPC1 injection.
- Positive blood test for antibodies to human immunodeficiency virus (HIV) types 1 or 2, antibodies to hepatitis B virus (HBV) core antigen or antibodies to hepatitis C virus (HCV)
- 14. Panel reactive antibodies (PRA) ≥ 20%; if a site lab reports PRA only for HLA Class I or separately for HLA Class I and II, exclusion will be based solely on the PRA for HLA Class I
- 15. Serum creatinine >1.5X above the established limit for the normal range at individual study center laboratories at baseline
- 16. Blood levels of aspartate aminotransferase (AST) or alanine aminotransferase (ALT) > 3X the established upper limit for the normal range at individual study center laboratories at baseline
- 17. Hematocrit below the study center lower limit for elective surgery at baseline
- 18. Positive blood cultures (48 hour culture results at Day -1)
- 19. Active untreated viral, fungal or bacterial infection at baseline
- 20. Evidence of surgical site infection at intended AST-OPC1 injection site at baseline
- 21. Temperature ≥ 38.6°C at two time points from Day -1 through Injection Day prior to surgery for AST-OPC1 injection

- 22. Body mass index (BMI) > 35 or weight > 300 lbs.
- 23. Active participation in another experimental procedure/intervention
- 24. Psychoactive substance use disorder (as defined by DSM-5) at any time during the 3 months preceding study entry
- 25. History of untreated or poorly controlled major depression, schizophrenia, paranoia, or other psychotic disorder as defined by DSM-5
- 26. A subject who, in the opinion of the investigator, is unlikely to return for all followup visits as specified in the protocol
- 27. Any condition that, in the judgment of the investigator, would preclude successful participation in the study

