6.4 AST-OPC1 Administration

One day prior to the planned injection of AST-OPC1 (i.e., Day –1), subjects should have any ongoing pharmacological DVT prophylaxis suspended in preparation for surgery. These may be restarted on Day 1.

Surgery to inject AST-OPC1 must be delayed if the subject has a temperature \geq 38.6°C at any 2 time points between Day –1 and Injection Day prior to surgery. Depending upon the duration of the delay of treatment, the Medical Monitor may request that certain baseline tests be repeated.

On Injection Day subjects will receive the dose of AST-OPC1 as determined by cohort assignment (Table 6-1). AST-OPC1 may only be administered by a licensed surgeon who has both training and experience in performing intradural surgical procedures on the spine. In addition, each surgeon must be trained and qualified by the Sponsor on the use of the SPD and the injection procedure prior to their first administration of AST-OPC1 (see Appendix C).

Cohort	Dose (# of cells)	Concentration (cells/µL)	Volume per Injection (µL)	Number of Injections	Total Volume Administered (μL)
1	2 x 10 ⁶	4 x 10 ⁴	50	1	50
2	1 x 10 ⁷	2 x 10⁵	50	1	50
3	2 x 10 ⁷	2 x 10⁵	50	2	100
4	1 x 10 ⁷	2 x 10⁵	50	1	50
5	2 x 10 ⁷	2 x 10⁵	50	2	100

 Table 6-1:
 AST-OPC1 Dose Cohorts and Injection Preparation

The injection procedure requires an open or minimal-access surgical exposure from a posterior approach with the subject sedated under general endotracheal anesthesia. Neuromuscular paralyzing agents will also be administered to prevent subject movement during the injection procedure. This is necessary because if a subject moves while the needle is in the spinal cord, additional damage to the adjacent spared spinal cord tissue could occur.

It is recommended that the surgeon and anesthesiologist consider the placement of an arterial line for intraoperative blood pressure monitoring, since this could facilitate rapid detection and management of an episode of intraoperative autonomic dysreflexia. For subjects with incomplete SCI (i.e., AIS-B), intraoperative monitoring of somatosensory evoked potentials is recommended to determine whether these are adversely affected by the injection procedure.

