7.1 Screening (Days –11 to –3)

Tests and procedures to confirm eligibility (see Section 4) are summarized below. Tests may be conducted between 11 and 3 days prior to the planned day of surgery for AST-OPC1 injection unless otherwise noted.

Note: if the day of injection is subsequently delayed, all screening tests and procedures that are not repeated will still be deemed to have been collected within the appropriate pre-operative window.

- Obtain demographic data
- Past and current medical history
- Complete physical exam and vital signs
- ISNCSCI exam
- MRI (cervical spine and brain, with and without gadolinium-DTPA contrast) between Days –7 and –3
- ECG
- Hematology (CBC with differential, RBCs, hematocrit, platelets)
- Blood chemistry (albumin, alkaline phosphatase, ALT, AST, BUN, calcium, chloride, creatinine, glucose, magnesium, phosphorus, potassium, total protein, sodium, total bilirubin)
- Serology for HIV antibody, Antibody to Hepatitis B core antigen, and Hepatitis C virus antibody
- Panel reactive antibodies
- Serum pregnancy test for females of childbearing potential
- 48-hour blood cultures (to be drawn on Day -3)
- Concomitant medications
- Adverse events

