7.2 Baseline (Days –2 to –1)

Note: As indicated below, some of the baseline assessments may be performed as early as

Day -4 if required to accommodate clinical site staff availability.

- Brief physical exam and vital signs (check vital signs both days)
- Standard neurological exam (may be performed on Day -4 to -1)
- ISNCSCI exam (may be performed on Day -3 to -1, unless the screening ISNCSCI was performed on Day -3.)
- Partial Graded Redefined Assessment of Strength, Sensibility and Prehension (GRASSP; may be performed on Day -4 to -1)
- Spinal Cord Independence Measure (SCIM; may be performed on Day -4 to -1)
- Hematology (as before)
- Blood chemistry (as before)
- Fasting blood glucose (may be done pre-op on injection day)
- Blood for HLA typing (may be obtained on Day -4 to -1)
- Blood for immune response monitoring (may be obtained on Day -4 to -1)
- Blood for xenotransplantation archival (may be obtained on Day -4 to -1)
- Withhold pharmacological DVT prophylaxis on Day -1
- Concomitant medications
- Adverse events

If the day of injection is delayed, some or all of the following tests and procedures may need to be repeated prior to the new Injection Day. The determination of which tests and procedures to be repeated will be made by the Investigator after consultation with the Sponsor's Medical Monitor.

Note: baseline tests and procedures that are not repeated will still be deemed to have been collected within the appropriate pre-operative window.

- Brief physical exam and vital signs
- Brief ISNCSCI exam
- MRI (cervical spine, non-contrast only)
- Hematology (as before)
- Blood chemistry (as before)
- Concomitant medications
- Adverse events

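### Two temperatures of 38.6°C or more before surgery exclude a subject in Protocol Section 4.2 but delay surgery in Section 6.4, and after a delay exclusion 18 can be cleared on a culture drawn before the fever

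*Protocol*

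**What the plan says.** **Fever.** Exclusion 21 in Protocol Section 4.2, repeated in the synopsis, reads "Temperature ≥ 38.6°C at two time points from Day -1 through Injection Day prior to surgery for AST-OPC1 injection". Section 6.4 says "Surgery to inject AST-OPC1 must be delayed if the subject has a temperature" of 38.6°C or more "at any 2 time points between Day –1 and Injection Day prior to surgery". It adds: "Depending upon the duration of the delay of treatment, the Medical Monitor may request that certain baseline tests be repeated".

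**Blood culture.** Exclusion 18 in Section 4.2 is "Positive blood cultures (48 hour culture results at Day -1". Section 7.1 and Table 7-1 schedule one culture, drawn on Day -3 as a screening test.

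**What happens to tests after a delay.** The Section 7.1 note says that if injection is delayed, "all screening tests and procedures that are not repeated will still be deemed to have been collected within the appropriate pre-operative window". Section 7.2 has a matching note for baseline tests. It also lists procedures that may need repeating: brief physical exam and vital signs, brief ISNCSCI, non-contrast cervical MRI, hematology, chemistry, concomitant medications and adverse events. Blood culture is not on that list.

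**Related provisions.** Section 5 enrolls subjects who are eligible under Section 4. The opening of Section 7 defines Injection Day as the day the product is injected and numbers the other days from it. Section 7.3 starts tacrolimus 6 to 12 hours after injection.

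**The concern.** One observation carries two consequences. Under exclusion 21 the subject is ineligible; under Section 6.4 the subject waits and may be treated. Neither section refers to the other, and no rescreening rule turns the exclusion into a deferral. Two sites could handle the same patient differently, each with a passage to rely on. The SAP deviation categories (Section 6.1.2) include unmet eligibility, so the same conduct could also be classed differently.

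The delay route has a second gap. Fever is the one reason for delay that Section 6.4 names, and the scheduled culture was drawn before the readings that caused the delay. Followed as written, Sections 6.4 and 7.1 let a subject have intradural surgery and start tacrolimus with exclusion 18 cleared on that culture. What is at stake is consistent eligibility and the safety screen before surgery. No sample size, estimate or interval in the SAP changes.

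**Working it through.** The plan states no figure on this point, so the check compares passages and counts days.

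**Step 1. Compare the fever rules.**

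| Element | Exclusion 21 (4.2) | Section 6.4 |
|---|---|---|
| Threshold | 38.6°C or more | 38.6°C or more |
| Readings | two | two |
| Window | Day -1 to surgery | Day -1 to surgery |
| Consequence | excluded | surgery delayed |
| Refers to the other section | no | no |

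Only the consequence differs.

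**Step 2. Order of events on the original schedule.** The culture is drawn on Day -3 and its 48-hour result falls on Day -1. The qualifying temperatures are taken from Day -1 up to surgery. The draw therefore always precedes them.

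**Step 3. Age of the accepted culture.** Let d be the delay in days. The culture was drawn 3 days before the original date, so its age at injection is 3 + d days.

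- No delay: 3 + 0 = 3 days.
- Both readings on the original Day -1, or one on each day: a 1-day delay leaves fewer than two of them in the new window. Age 3 + 1 = 4 days.
- Both readings on the original Injection Day: a 1-day delay makes that day the new Day -1, still in the window, so at least 2 days are needed. Age 3 + 2 = 5 days.
- Longest delay inside the 21-42 day window (exclusion criteria aside, inclusion criterion 7): planned for post-injury day 21, injected on day 42, d = 42 - 21 = 21. Age 3 + 21 = 24 days. Check: drawn on post-injury day 21 - 3 = 18, and 42 - 18 = 24.

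The short-delay cases assume no further qualifying readings. At no point from 4 to 24 days does the text require a culture drawn after the fever.

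**Step 4. Try each way of counting Day -1.**

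| Day -1 counted from | Exclusion 21 | Exclusion 18 |
|---|---|---|
| Original Injection Day | Subject stays excluded, so the Section 6.4 delay leads nowhere | Cleared on the original culture |
| Actual Injection Day | Old readings can leave the window, so Section 6.4 works | Original result falls on Day -(1 + d), not Day -1; only the Section 7.1 note makes it acceptable |

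Neither way of counting settles both exclusions. The one that reconciles the fever rules is the one under which exclusion 18 depends on the Section 7.1 note.

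**The case against.** The best reply is that the fever rules can be read together. Both forbid surgery on the affected date. Section 7 ties Injection Day to the day of actual injection, so a postponed date was never Injection Day and the exclusion 21 window moves with the surgery. Section 6.4 then says what to do in the meantime. This is a fair reading, and it means that a reader who infers that no site could comply with both passages goes too far. What stands is that the protocol does not state this reading, and Step 4 shows that it leaves exclusion 18 resting on the Section 7.1 note.

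A reader might also infer that a repeat culture is barred, or that Section 6.4 limits repeats to baseline-visit tests. The documents do not support this. The Section 7.1 wording presupposes that screening tests can be repeated, and the Section 7.2 list already includes MRI, which before injection is otherwise scheduled only at screening. A repeat culture is simply not required.

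Nor do the documents leave infection unscreened. Exclusions 19 (untreated active infection), 20 (infection at the surgical site) and 27 (investigator judgment) remain. Vital signs, physical exam and hematology may be repeated, and vital signs are taken on Injection Day. These safeguards are partial: 19 and 20 apply at baseline, and the Section 7.2 note accepts baseline procedures that are not repeated.

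Two further inferences fail. Sections 6.4 and 7.2 do not conflict on who decides: the Medical Monitor may ask for repeats, and the Investigator decides after consulting the Medical Monitor. It is also not shown that an infection present before injection would enter the primary endpoint as related. Section 10.1.3 leaves relatedness to the Investigator and classes as unrelated an event that other factors explain. SAP Section 6.2.2 counts an event that began before injection as treatment-emergent only if it worsens afterwards.

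**Conclusion.** The point holds as an inconsistency that should be reconciled. The same temperature finding is an exclusion in Section 4.2 and a cause for delay in Section 6.4, with nothing to say which governs. After a delay, exclusion 18 can be formally cleared on a culture that predates the fever, about 4-5 days old after a short delay and at most 24 days old.

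The second part arises only if a site follows Section 6.4 and does not repeat the culture. It would be wrong to say that such a subject breaches exclusion 18: on the text of Section 7.1 the criterion is cleared, and that is the difficulty.

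The 24-day figure is an extreme that needs the earliest planned date and the latest permitted one. It could apply to few subjects. The rationale for Amendment 3 reports 17 already dosed when the window became 21-42 days, and SAP Section 3.2.1 reports 25 in all, so at most 25 - 17 = 8 were dosed under that window. The documents do not show that any subject was delayed for fever.

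**What to change.** 1. Reconcile exclusion 21 (Section 4.2 and synopsis) with Section 6.4, so that two qualifying temperatures have one stated consequence and each passage refers to the other. If the consequence is deferral, state how eligibility is re-established.
2. Reconcile the delay notes in Sections 7.1 and 7.2 with the Day -1 timing in exclusion 18. State whether that timing runs from the original or the actual Injection Day, and whether the notes override a criterion that carries its own timing.

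Which clinical rule applies, and whether a culture is repeated, is for the sponsor to decide.

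The cost is a few sentences in Sections 4.2, 6.4, 7.1 and 7.2 and the synopsis. SAP Section 3.2.1 reports that enrollment closed in December 2017, so for the 25 treated subjects the practical step is to use the deviation review in SAP Section 6.1.2 to identify any injection delayed for fever and classify all such cases the same way. That uses data already collected.

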5 ENROLLMENT

Site personnel should notify the Sponsor when screening initiates for an individual subject in order to ensure that the protocol specified rules for staggering within cohorts and for advancement to Cohorts 2-5 are followed correctly. This notification will also enable the Sponsor to ensure that the maximum number of subjects per each cohort is not exceeded.

After signing informed consent, potential subjects will be assigned a subject identification containing the site number and a sequential enrollment number. After eligibility assessment, subjects who are deemed eligible in accordance with the inclusion/exclusion criteria (Section 4) will be enrolled into the study.

6 STUDY TREATMENTS

6.1 Investigational Product

AST-OPC1 is a cryopreserved cell population containing a mixture of oligodendrocyte progenitor cells and other characterized cell types that are obtained following differentiation of uhESCs. At the time of cryopreservation, each vial contains 7.5×10^6 viable cells in 1.2 mL of cryoprotectant solution.

AST-OPC1 is supplied in 2.0 mL cryovials and is shipped to the clinical sites in the vapor phase of liquid nitrogen. The cryopreserved vials of AST-OPC1 should be stored in the vapor phase of liquid nitrogen in a validated storage tank.

Each clinical site will be supplied with AST-OPC1 starter kits and dose preparation kits by the Sponsor. These kits consist of reusable or disposable laboratory items required for the preparation of AST-OPC1 doses and are assembled by a contract manufacturing organization. Sites will also receive a reusable syringe positioning device that is required for AST-OPC1 injection. The starter kits, dose preparation kits, and syringe positioning devices should be stored at room temperature.

6.2 Dose Preparation

Prior to administration, AST-OPC1 will be thawed and prepared according to instructions for preparation by study personnel who have been trained in the AST-OPC1 dose preparation procedure. The dose preparation procedure is shown graphically in a process flow diagram provided in Appendix B and is described below. AST-OPC1 dose preparation may only be performed in a facility qualified for this purpose by the Sponsor and only by personnel who were previously trained and qualified by the Sponsor.

Dose preparation kits consist of presterilized, single-use disposable items required to prepare the AST-OPC1 dose. Dose preparation begins with the thawing of an appropriate number of vials of AST-OPC1. The thawed cells are washed and suspended in Isolyte[®]S and 1% HSA. A sufficient number of cells will be loaded into the 0.25 mL delivery syringe using an 18-gauge blunt loading needle in order to enable delivery of the assigned dose while taking into account the residual dead volume in the syringe and needle.

The loaded delivery syringe is sealed using a syringe Luer-Lok[®] cap, and labeled with the date prepared, drug name, dose concentration, and expiration time for the dose. The syringe is then placed in a sealable sterile pouch. The cap protects the prepared dose from unintentional ejection of cells. The pouch containing the secured syringe is then placed

inside a refrigerated (2-8°C) AcuTemp[®] PX1L container. The AcuTemp[®] container is secured by the use of a one-way plastic zip-tie mechanism with a tag label containing the subject information, date prepared, drug name, dose concentration, and expiration time for the dose.

Based upon data from stability studies of prepared doses, AST-OPC1 formulated in Isolyte[®]S and 1% HSA may be stored for up to 12 hours at refrigerated temperature (2-8°C) in the AcuTemp[®] PX1L container plus up to an additional 3 hours at room temperature prior to administration.

